Phase 2 Study of Teriparatide for the Treatment of Idiopathic Osteoporosis in Premenopausal Women

IRB AAAF2251 Protocol Version 3.2

1. Study Purpose and Rationale

Osteoporosis is a skeletal disorder characterized by reduced bone strength that predisposes to an increased risk of fracture^{1,2}. Osteoporosis affects postmenopausal women and elderly men and is very unusual in healthy individuals under age 50. Moreover, more than 90% of young men and premenopausal women with osteoporosis have a secondary cause of bone loss³, such as an underlying disorder (e.g., hypogonadism) or a medication exposure (e.g., glucocorticoids, antiepileptic drugs), that either interfered with acquisition of peak bone mass or caused excessive bone loss thereafter³⁻¹⁵. Idiopathic osteoporosis (IOP) is defined as osteoporosis that affects young, otherwise completely healthy individuals with intact gonadal function and no secondary cause of bone loss. First described by Fuller Albright in 1944¹⁶, IOP is an uncommon condition with an estimated annual incidence of 0.4 cases per $100,000^3$. IOP predominantly affects Caucasians, who generally present in their mid-30s with one more low trauma fractures¹⁷. In the course of an NIH-funded study of premenopausal women with IOP (R01 AR49896, IRB AAAA9245), we have shown that women with IOP have low areal bone mineral density (aBMD) at the spine, hip and forearm compared to normal women⁷⁹. Additionally, using noninvasive high resolution imaging of the central and peripheral skeleton and detailed analyses of transiliac crest bone biopsies, we identified several distinctive and consistent features of bone quality in premenopausal women with IOP: thin cortices, lower trabecular volumetric bone mineral density (vBMD), fewer trabecular plates, fewer and longer trabecular rods, decreased connectivity between rods and plates, lower mineralization density and lower estimated stiffness of cancellous bone^{80, 81, 82, 83}. Bone remodeling and biochemical indices of mineral metabolism did not differ between IOP subjects and controls ⁸².

Although not every woman with IOP requires pharmacologic intervention, many have sustained multiple low-trauma fractures or have extremely low bone mineral density (BMD). There is currently no FDAapproved therapy for IOP in premenopausal women and a safe and effective therapy is urgently needed. Bisphosphonates are one therapeutic option, but the associated gains in BMD are primarily due to reduction in the remodeling space and increased mineralization of bone rather than improvements in microarchitecture. This is an important consideration as microarchitectural deficits are a consistent feature of IOP in premenopausal women, while remodeling activity is most commonly normal or low. Furthermore, potential teratogenic effects limit the safety of bisphosphonates in premenopausal women.

Osteo-anabolic therapy with human recombinant parathyroid hormone 1-34, hPTH(1-34) or teriparatide (TPTD), terms which will be used interchangeably in this proposal, has been shown to improve bone mass and microarchitecture in postmenopausal women and is approved for men with primary or idiopathic osteoporosis, as well as men, premenopausal and postmenopausal women with glucocorticoid-induced osteoporosis. In contrast to bisphosphonates, TPTD increases bone formation and BMD, and increases bone strength by improving bone microarchitecture¹⁸⁻³⁵. Moreover, TPTD has been shown to increase BMD in men with IOP³⁶, in premenopausal women with glucocorticoid-induced osteoporosis (GIOP)^{37,38} and to prevent bone loss in premenopausal women with nafarelin-induced acute estrogen deficiency ^{84.} In addition, we have recently completed a pilot study of TPTD in 21 premenopausal women with IOP, in which there were marked improvements in areal BMD by DXA at the lumbar spine, femoral neck and total hip and bone microarchitecture and estimated strength at the iliac crest over 18-24 months of therapy ^{72,73,76, 85}. Using high resolution CT imaging, we also found that TPTD increased volumetric BMD and estimated strength at the distal radius and tibia in the same women.

The major objective of this protocol is a therapeutic one, namely to establish the safety and efficacy of TPTD in premenopausal women with IOP in a phase 2 clinical trial. We hypothesize that osteo-anabolic therapy with TPTD will improve areal and vBMD in premenopausal women with IOP. We also hypothesize that TPTD will restore abnormal microarchitecture toward normal and improve other aspects of bone quality in premenopausal women with IOP. The primary aim of this research study will be to establish the efficacy and safety of 6 months of TPTD versus placebo in premenopausal women with IOP. Secondary aims are to determine the extent to which 12 and 24 months of TPTD improves areal and volumetric BMD, bone microarchitecture and stiffness compared to baseline measures in premenopausal women with IOP and to determine whether baseline bone turnover, as assessed by quadruple tetracycline labeling predicts response to TPTD. This study will have high impact on clinical practice as it pertains to the management of premenopausal women with IOP. This study is exploratory and will not support any new labeling claims for Forteo in the premenopausal patient population.

For the sub-study: We aim to investigate the pharmacokinetics (pK) and pharmacodynamics (pD) of teriparatide (Forteo) to determine if subject weight influences pK or pD. To develop preliminary data necessary to plan larger studies on this issue, we aim to study 6 subjects already enrolled in this study (AAAF2251) who are already in the open label treatment period. We will enroll 3 normal weight subjects (BMI between 18.5 kg/m2 and 24.9 Kg/m2) and 3 overweight or obese subjects (BMI equal to or greater than 25 kg/m2). All subjects will be offered participation until enrollment goals for the sub-study will be met.

Previous studies have shown that the increases in BMD observed in response to TPTD may dissipate over time if patients are not placed on antiresorptive therapy after TPTD is discontinued. However, other studies suggest that this dissipation does not occur in women receiving estrogen. Studies in postmenopausal women on estrogen found that hPTH(1-34) increased aBMD at the LS and at the hip^{19,33}, and resulted in major reductions in vertebral fracture¹⁹. Importantly, BMD remained stable in postmenopausal women on estrogen followed for two years after TPTD discontinuation¹⁹. Lane et al. reported similar results in postmenopausal women with GIOP on estrogen²⁶. Although no studies have evaluated duration of TPTD effects in menstruating premenopausal women with IOP, an extension study of hPTH(1-34) in premenopausal women with endometriosis receiving nafarelin found that the benefits of in hPTH(1-34) persisted in women who regained normal menses⁸⁶. These three studies suggest that in estrogen-replete premenopausal women with IOP, increases in bone mass resulting from TPTD would be sustained after the course of therapy is completed. However, we recently analyzed new data from our open-label pilot study of 21 premenopausal women with IOP who were treated with 18-24 months of TPTD, 20 mcg daily⁸⁵. Specifically, 2-year follow-up data on 15 of the 21 women, has revealed that nine (60%) have sustained significant bone loss (7.4 + 3.1%) at the lumbar spine, although they have maintained the gains at the hip; six women have maintained their gains.

[figure not shown]
We believe that these data require an amendment to the study design of R01 FD 009302, Teriparatide for Premenopausal Idiopathic Osteoporosis. The current study design includes 12 months of follow-up after the study subjects complete 24 months of TPTD. Instead of the current design, in which all subjects complete one year of observation after 24 months of TPTD, we would like to offer the subjects three choices:

- 1. One year of observation
- 2. To leave the study and be treated clinically with an antiresorptive drug to maintain gains in bone density after treatment with TPTD, which is the current clinical standard of care for postmenopausal women and men who have completed two years of TPTD therapy

3. Participation in a new study evaluating anti-resorptive therapy for prevention of bone loss after stopping TPTD. The new study is currently in the design phase and funding phase and precise details are not yet available

All currently enrolled subjects would be re-consented and future participants would sign a new informed consent document with the new study design.

On January 26, 2014, the Research Pharmacy informed the Principal Investigator that there was a mistake in the randomization table for the study. Subjects (n=40) should have been randomized 28:12, active Teriparatide to placebo, for 6 months, followed by a single-switchover design in which all would receive active drug. The randomization code in the table provided to the Research Pharmacy by the Study Statistician was reversed and the subjects were randomized 12:28, active Teriparatide to placebo. To date, 18 patients have been enrolled and randomized. Research Pharmacy has informed us that 12 subjects were randomized to placebo and 6 to active Teriparatide. As 12 subjects have already been randomized to receive placebo first, we will increase enrollment by one subject (total, 41) and generate an adaptive randomization table in which one of the 23 subjects yet to be enrolled will be randomly assigned to placebo and 22 will be randomly assigned to active Teriparatide. This will maintain the number of subjects treated with active drug at 28 and maintain blinding of subjects and study personnel to study assignment.

2. Study Design and Statistical Procedures

randomized, double blind, placebo-controlled, single switch-over trial of TPTD in premenopausal women with IOP. Forty-one subjects will be assigned to TPTD (Group A; n=28) or placebo (Group B; n=13). At the 6 month timepoint, all subjects will receive TPTD, but blinding of original group assignment will be maintained for an additional 6 months. At the 12 month visit, the blind will be broken and those initially randomized to TPTD (Group A) will continue on study drug for an additional 12 months while those initially randomized to placebo (Group B) will continue for an additional 18 months, so that subjects in both groups complete 24 months of treatment overall. aBMD by DXA and HRpQCT will be measured at baseline and at 6 month intervals. vBMD by cQCT will be performed before randomization and after 24 months of TPTD (Table 1). A quadruple labeled transiliac crest bone biopsy will be performed at 3 months for both Group A and B. Eli Lilly & Company will provide TPTD and placebo but will supply no other funding. After 24 months of treatment in either Group A or B, all women will be offered three choices for follow up: the subjects can A) continue to to be followed for 12 months off TPTD B) choice to leave the study and be treated clinically using an anti-resorptive medication to maintain gains in bone density after treatment with TPTD, or C) join a new study to maintain gains in bone density after treatment. The new study is currently in the design phase and funding phase and precise details are not yet available.

Statistical Analysis Plan

2.A. Statistical Analysis Plan Our aims in this protocol are as follows:

Aim 1: To establish the efficacy and safety of 6 months of TPTD versus placebo in premenopausal women with IOP

Aim 2: To determine the effect of 3 months of TPTD on bone remodeling at the tissue level and the extent to which baseline and 3 month bone remodeling predicts response to TPTD in premenopausal women with IOP.

Aim 3: To determine the extent to which 12 and 24 months of TPTD improves areal and volumetric BMD, bone microarchitecture and strength (stiffness) compared to baseline measures in premenopausal women with IOP

Prior to statistical analysis, all outcome and covariate data will be summarized with descriptive statistics, outliers examined, distributions identified and normalizing transformations applied where indicated. All of the above analyses will be based upon the intention-to-treat principle. The missing data mechanism (MCAR, MAR) for all outcomes and covariates will be assessed and, in the event of a non-ignorable mechanism, analyses will subjected to the methods of Diggle and Kenward³⁹ for continuous measures or Ibrahim and Lipsitz⁴⁰ for safety outcomes. Bone turnover markers will be log-transformed prior to analysis. Inferential testing will use a 5% two-tailed type I error rate with no adjustment for multiplicity taken for primary outcome analyses. Secondary efficacy analyses type I error rates will be adjusted by Bonferroni method whereas secondary safety analyses will not. In keeping with the objective of proposed exploratory analyses to generate data patterns consistent or inconsistent with improved bone quality, no adjustment for multiplicity will be taken. No interim efficacy analyses are planned. The statistical analysis plan will be modified to account for the adaptive randomization procedure, which is relevant to Aim 1 only.

AIM 1:

Primary efficacy outcome analysis: Analysis of covariance (ANCOVA) comparison of between-group (treated vs placebo) differences in mean change in LS aBMD (g/cm^2) by DXA from pre-treated baseline to 6 months of assigned treatment with adjustment for the following continuous baseline variables LS aBMD (g/cm^2), age (years) and weight (kg).

Primary safety outcome analysis: Fisher's Exact test of between-group difference in the number of people in each assigned group reporting at least one hypercalcemia or hypercalciuria event in the first 6 months of assigned treatment; followed by Cox proportional hazards model analysis of the between-group difference in the time-to-first hypercalcemia or hypercalciuria event; followed by GEE testing of the between-group difference in the temporal pattern of the repeatedly sampled hypercalcemia or hypercalciuria events in the first 6 months of assigned treatment.

Secondary efficacy outcome analyses: TH, FN and 1/3 Radius aBMD by DXA will analyzed by ANCOVA as described for the primary outcome, above.

Secondary safety outcome analyses: Fisher's Exact test will be used to assess treatment group differences in numbers of people endorsing each symptom reported on the symptom checklist administered at each study visit without adjustment for multiplicity. The GEE test approach proposed for the primary safety

outcome analysis of longitudinal events will be repeated for any symptom reported by >10% of either treatment group.

AIM 2:

Primary analysis: The between-group mean difference in the quad-labeled histomorphometric measured change in Mineralizing Surface (MdPm) and Bone Formation Rate (BFR/BS) at 3 months will be analyzed with ANCOVA with adjustment for the baseline continuous variables of age (years) and weight (kg.). Outcomes will be analyzed separately without adjustment for multiplicity. Secondary analyses: In the teriparatide-treated group the relationship between baseline MdPm and BFR/BS, and change in MdPm and BFR/BS in the first three months of treatment, and 12 and 24 month change in aBMD of the spine and hip by DXA and vBMD of the spine by cQCT will be assessed with multiple regression analysis. Per annum change in DXA and cQCT outcomes will be separately modeled as a function of baseline MdPm and BFR/BS, baseline level of the DXA or cQCT outcome, age, weight, bone microstructure by microCT of biopsy specimens, and change from baseline in MdPm and BFR/BS during the first three months. Other potential baseline predictors of DXA and cQCT response to teriparatide treatment will be explored with multiple regression to determine whether any clinical or constitutional measures supercede change in MdPm or BFR/BS in predicting bone change.

AIM 3:

Primary efficacy outcome analysis: Analysis by linear mixed models for repeated measures (LMM_R) of the within-group (TPTD) change in LS aBMD (g/cm²) by DXA from pre-treatment baseline with repeated measures at 12- and 24-months. (This is a growth curve model testing the hypothesis that the temporal trajectory of within-subject change in outcome differs from a random process.) The model estimates the fixed effect of time, random effects for subject, error and the quadratic and cubic values of time entered as random effects, continuous covariates for age and weight at baseline and with an AR(1) covariance structure. The random effects for higher-order factors for time model monotonic and U-shaped components of the growth curve. Model estimated within-subject differences between specific timepoints will be assessed when the fixed effect of time is statistically significant. The LMM_R model will be repeated for LS trabecular vBMD by cQCT after 24 months of teriparatide. Secondary efficacy outcome analysis: The same LMM_R analysis proposed for Aim 2 primary outcomes

will be used for secondary efficacy outcomes of TH, FN and $1/3^{rd}$ RD aBMD by DXA and HRpQCT after 12 and 24 months, and cQCT after 24 months of TPTD. These analyses will also be used to explore the pattern of change in serum BTMs (P1NP and CTx), between baseline and 24 months. Exploratory analyses will also be conducted to determine whether clinical factors such as age, BMI, body composition, and aspects of the growth hormone axis may predict BMD response to TPTD.

2.B. Power and Sample Size

We have based our power calculations upon the preliminary data generated from our recent pilot study of 22 women with IOP who were treated with teriparatide for 24 months. Our power estimates are based upon 40 women randomized to TPTD or placebo (28:12) with data for analysis, assuming a 10% drop-out and an alpha level of 5%.

AIM 1:

Primary efficacy outcome: For the primary endpoint of between-group difference in LS BMD at 6 months, power calculation assuming the proposed two-group ANCOVA and outcome correlation with baseline covariates of 0.3, we will have >90% power to detect a difference of $3.7 \pm 3.3\%$ in the TPTD-treated vs. $0.8 \pm 2.9\%$ in the placebo-treated group (placebo estimate based on interpolation from our preliminary data at 12 months). The estimated effect size is consistent with an annual TPTD-induced increases of 7.0-13.5% in studies by Arlot et al. in postmenopausal women, Langdahl et al. in premenopausal women with GIOP, and Kurland et al. in male IOP³⁶.

Primary safety outcome: For our primary safety outcome, the between-group difference in the number of people in each assigned group reporting at least one hypercalcemia or hypercalciuria event, we do not expect to have sufficient power to detect group differences in event rate because of the rarity of TPTD-related safety events observed in our pilot study and reported by others in the literature. Secondary efficacy outcome: For our secondary efficacy endpoints of between-group differences in TH, FN and 1/3R, our preliminary data suggest that we will not have sufficient power to detect between groups differences in these measures at 6 months, as the increases are less pronounced than at the LS. Secondary safety outcome: While we will closely examine the safety data, our small sample size provides minimal power to detect any but the most dramatic differences in safety profile between groups.

AIM 2:

Primary efficacy outcomes: For MdPm and BFR/BS after 3 months of TPTD, we base our effect size assumptions on the Lindsay et al²⁸ estimates of changes from baseline to 1-month of cyclic TPTD treatment (assuming these measures are virtually unchanged over 3 months in the placebo treated group). Lindsay reports cancellous BFR/BS increased from 0.008 ± 0.006 to 0.027 ± 0.018 (a standardized effect size of 1.42) and cancellous MdPm from 1.33 ± 0.95 to 3.78 ± 2.53 after 1 month (a standardized effect size of 1.28). With the proposed sample size, we will have over 90% power to detect difference comparable or larger than the increase in bone formation detected by Lindsay after 1-month of treatment. Secondary analyses to assess the predictability of DXA and cQCT changes from baseline and 3-month changes in BFR/BS and MdPm: The proposed sample size enables us to detect between 40% to 55% of the variance accounted for in the 12- or 24-month DXA or cQCT change and the baseline to 3-month change in BFR/BS or MdPm (assuming 80% power, 5% alpha and a multiple regression model with up to 3 covariates partialled from both the bone density outcome and the histomorphometric predictor).

AIM 3:

Primary efficacy outcomes: For LS aBMD by DXA after 12 and 24 months of TPTD, we will have >86% power to detect changes from baseline. We based our estimate of LS aBMD at 12 months on our preliminary data, and at 24 months on the data of Graeff et al.⁴¹ who detected a 10.2% increase in aBMD over 24 months. We anticipate that the increase between baseline and 12 months will far exceed the increase from 12 to 24 months, which may not be statistically significant. For trabecular vBMD at the spine by cQCT after 24 months of TPTD, the work of Rehman et al.³², who detected an increase of 35% in vBMD, suggests that we will have power of >99% to detect within-group changes.

Secondary efficacy outcomes: We will have 99% power to detect within group increases from baseline in TH BMD at 12 and 24 months. This estimate is based upon our preliminary data. We do not have 24 month data; however, published work by Saag et al.⁴² and Keaveny et al.⁴³ suggests that we may not have sufficient power to determine whether TH BMD increases significantly between 12 and 24 months. In addition, we may not have sufficient power to detect significant changes in FN or 1/3R BMD. For HR-pQCT measures, the Bogado study⁴⁴ indicates we will have 99% power to detect within group changes in Ct.Th, Tb.N and Tb.Sp.

3. Study Procedures

3.A. Schedule of Visits

Visit 1 (Screening): Women with IOP fulfilling preliminary eligibility requirements (Telephone Questionnaire) will be invited to attend a Screening Visit at CUMC or Creighton. Prior to initiation of any screening procedures, an informed consent discussion will take place. Only after the informed consent (Screening Consent Form) is signed will screening procedures commence.. The visit will be scheduled during days 1-5 of the menstrual cycle to identify women in early menopause (FSH>20 mIU/ml). After a

negative pregnancy test, all will have BMD, VFA and body composition by DXA. Women who fulfill BMD or fracture eligibility criteria will complete a Historical Questionnaire (Appendix 1) on medical and reproductive history (menstrual history, menarchal age, parity, OCP use), risk factors for osteoporosis (eating disorders, alcohol, tobacco, caffeine intake), personal and family history of fractures, current and past medications. The Eating Disorder Examination - Questionnaire (EDE-Q; Appendix 2) will be given to identify women with subclinical eating disorders^{45,46}. All will have a standardized physical (weight, height by Harpenden stadiometer) by a physician co-investigator and a Secondary Osteoporosis Evaluations (SOPEval). The following must be normal: blood count, Westergren ESR, C-reactive protein, electrolytes, creatinine, thyroid and liver function tests, uric acid, calcium, phosphate, 25-OHD (>20 ng/dl; those with levels between 21-29 ng/ml will be offered supplementation to achieve levels >30), intact PTH (<65 pg/ml), tissue transglutaminase IgA antibody (tTG; 99% specific and 95% sensitive for celiac disease) and immunoglobulin A (IgA) to exclude celiac disease, 24-h urine for creatinine, calcium (<300mg/gCr) (100-250 mg), free cortisol. Other tests may be performed if less common etiologies are suspected. In some cases, arrangements may be made for some portions of the screening visit procedures (eg laboratory studies) to take place outside of this medical center. In all cases, eligibility will be verified by study physicians.

Visit 2 (Imaging): If the SOPEval is normal, candidates will be invited to proceed with Visit 2. Prior to initiation of any additional study procedures, an informed consent discussion will take place. Only after the informed consent (Study Consent Form) is signed will further research related procedures commence. The study will be described, including the bone biopsy procedure. Participants with fractures will be asked to bring verification (x-rays or radiology reports). They will complete standardized questionnaires to assess current diet and physical activity. We use the validated Block food frequency questionnaire (FFQ; Appendix 3)^{47,48} to assess calcium intake. Physical activity is assessed by the modified Baecke questionnaire (Appendix 4)⁴⁹⁻⁵¹. Equivocal VFA results will be evaluated with spine x-rays. Central QCT of the spine (L1 and L2) with additional single slice at L4, and HR-pQCT of the distal radius and tibia will be performed to measure volumetric BMD, body composition (subcutaneous and visceral adiposity), and cortical and Tb microstructure. Serum will be archived at -80°.At this visit, subjects will also receive tetracycline for their first round of antibiotic labeling and instructions with a scheduled dosing according to protocol. Subjects will complete labeling before the randomization visit, where they will receive Forteo and begin treatment.

52,53

Visit 3 (Randomization): During this visit, imaging results will be reviewed with the subjects. Eligible subjects who agree to participate will be randomized to TPTD or placebo (ratio 28:13) through block randomization with randomly varying block sizes of 2, 4 or 6, stratified by whether they are included on the basis of history of fractures or low BMD. Serum/urine will be archived at -80°C for batch analyses of specialized biochemistries. DNA will be obtained from peripheral blood lymphocytes for archival purposes. We will collect blood for the measurement of osteoblasts, or bone building stem cells, in the bloodstream.

Subjects will be provided with calcium (citrate) caplets (Citracal + D; each 315 mg + 250 IU D) and a multivitamin (Centrum) that provides 500 IU of vitamin D daily. Most subjects will be instructed to take 2 Citracal caplets and a multivitamin; the total daily dose of calcium from supplements will be approximately 630 mg and of vitamin D 1000 IU. Subjects with very low dietary calcium intake (<500 mg/d estimated by interview and the FFQ), will be asked to take 3 Citracal caplets, while those with high dietary calcium intakes (>1,000 mg/day) will be asked to take 1 Citracal caplet.

Visits 4-5, 8-13 (Study Evaluations): At each study visit, study coordinators will assess any adverse events that transpired since the last study visit. Patients will be instructed to bring their Forteo journal and pens with them to every visit, which documents their compliance with the study medication. The purpose

of the 1-week and 1-month visits (Visits 4 & 5) is to monitor for compliance and adverse effects. At the 1-week and 1-month visit, we will also obtain fasting serum for serum calcium (safety) and at the 1-Month we will also collect serum for BTMs. These visits may be conducted on site for women who reside close to the study sites or may be a telephone contact and local blood draw for those who live at a distance. The remainder of the study visits to perform imaging studies and/or blood draws and dispense study drug are shown in Tables 1-3. We will perform a single follow-up cQCT scan after 24 months of TPTD treatment to minimize radiation exposure in these women who are of child-bearing age. At Visit 12, subjects will be presented with three options for post-TPTD follow up as described in the study design.

Visit 6 (Pre-Biopsy Clearance and Labeling): Subjects will have a pre-biopsy clearance visit with the surgeon and have safety bloods drawn and processed as per hospital regulations. Subjects will receive their second antibiotic labeling agent, demeclocycline, and accompanying labeling schedule.

Visit 7 (Transiliac Bone Biopsy): Transiliac crest bone biopsy is used to investigate 3-dimensional bone structure and static indices of bone remodeling. Dynamic remodeling indices (e.g., mineralizing surface and bone formation rate) are also assessed with tetracycline labeling techniques. The traditional double label biopsy protocol involves administration of two 3-day courses of tetracycline separated by 12 days. Tetracycline localizes on bone surfaces undergoing active bone formation and permits precise quantification of the rate of bone formation and remodeling. In the quadruple labeling protocol, 2 sets of double tetracycline labels are administered: one set before drug treatment, and a second set after 1-3 months of treatment/placebo; a single biopsy is then performed after the second set of labels (74). Because two different tetracyclines are used that fluoresce in different colors, a single biopsy can be used to assess dynamic indices of bone remodeling before and during drug treatment. This labeling protocol has been previously used by our group to study the osteoanabolic effects of TPTD in postmenopausal women (74) and the effects of hPTH(1-84) in subjects with hypoparathyroidism (75).

Transiliac crest bone biopsy will be performed according to procedures established at CUMC and Creighton. We will be performing the quadruple labeled bone biopsy at the 3 month visit. We have a long track record of performing research quality, bone biopsies and have been successful in obtaining bone biopsy specimens in both normal and abnormal cohorts of subjects, including women with IOP.

Table 1: Study	1	2	3	4	5	6	7	8
Visits	Screen	Imagin	Randomiz	1W	1M	2M	3M	6M
		g	e			Labelin	Biops	
						g	у	
Consent	Х	Х						
MD Visit	Х	Х				x ^a		х
Dispense TPTD			х				X	х
Telephone Contact [#]				Х	Х	X	X	х
Pregnancy Test	Х	Х	Х					х
BMD by DXA	Х							х
History & Physical	Х							
Questionnaire A & B	Х							
Questionnaire C & D		Х						
Adverse Events				Х	Х		X	X

Serum FSH	x								
SOPEval [%]	X								
HR-pQCT	Λ	X							x
Central QCT									A
VFA by DXA	X								
Body Composition by									
DXA	Λ								
Blood/Serum Archive		x ^β	5	x ^β		x		x	x
24H urine	х					X			x
calcium/creatinine									
Calciotropic				х					
Hormones									
Bone Turnover				х		х		X	x
Markers									
Pre-Biopsy Labs							X		
Antibiotic Labeling		X					X		
Bone Biopsy								X	
		-		1) for safety	1400
Table 2: Study Visits –	9	10	11	12	13				
Group A*	9M	12M	18M	24M	36M				
MD Visit		X	V	X	X				
Dispense TPTD		X	X X	X					
Telephone Contact [#]	X	X	X X	X	X				
Pregnancy Test BMD by DXA		X	X X	X	X				
History & Physical		X	Λ	X	X				
Adverse Events	v	X	Х	X	X				
Serum FSH	X	X	Λ	X	X				
HR-pQCT		x		X	X				
Central QCT		Λ		X X	Λ				
VFA by DXA		x		X	x				
		X	X	X	X				
Calciotropic Hormones		X		X	X				
Bone Turnover Markers		X	Х	X	X				
* Only for treatment									
treatment (Group A # Will occur before		luled visi	t						

Table 3: Study Visits – Group B**	9 9M	9 12M	10 18	11 24	12 30	13 42
Group D	>	12111	M	M	M	M
MD Visit		х		Х		Х
Dispense TPTD		Х	Х	Х		
Telephone Contact [#]	Х	X	Х	Х	Х	Х
Pregnancy Test		х	х	х	Х	Х
BMD by DXA		х	Х	Х	Х	Х
History & Physical		х		Х		Х
Adverse Events	х	х	Х	Х	Х	Х
Serum FSH					Х	
HR-pQCT			х		Х	Х
Central QCT					Х	
VFA by DXA		х		х		Х
Blood/Serum Archive	х	х	х	х	Х	Х
Calciotropic Hormones		х		Х		Х
Bone Turnover		х	Х	Х	Х	Х
Markers						
** Only for treatment group that started with 6 months of						
placebo injections (Group B)						

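### The corrective 22:1 allocation leaves blinding of study personnel only nominal for 23 of the 41 women, although the protocol says blinding is maintained

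*Combined protocol and SAP*

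**What the plan says.** Section 1 (Study Purpose and Rationale) gives the history. The plan was: "Subjects (n=40) should have been randomized 28:12, active Teriparatide to placebo, for 6 months". The code was reversed. At the time of writing, "To date, 18 patients have been enrolled and randomized", and the research pharmacy had told the study team that "12 subjects were randomized to placebo and 6 to active Teriparatide". Under the corrective table, "one of the 23 subjects yet to be enrolled will be randomly assigned to placebo and 22 will be randomly assigned to active Teriparatide". The paragraph concludes that this will "maintain blinding of subjects and study personnel to study assignment".

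Section 2 (Study Design and Statistical Procedures) still calls the trial double blind, with 28 women on TPTD and 13 on placebo. All women receive TPTD from month 6, but original assignment stays masked until month 12: "At the 12 month visit, the blind will be broken".

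Section 4 (Study Drugs or Devices) provides pens that look the same and leaves the allocation with the research pharmacist. Section 3.A (Visit 3) describes 28:13 block randomization and does not mention the 22:1 table. Section 2.A says that the analysis plan will be modified for the adaptive procedure, but gives no modification and does not discuss predictability.

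Among the Aim 1 secondary safety analyses, Section 2.A compares the "numbers of people endorsing each symptom reported on the symptom checklist administered at each study visit". Section 3.A has study coordinators assess adverse events at the study visits.

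**The concern.** A blind can fail without any code being disclosed, if the allocation ratio is so lopsided that the arm is nearly certain. The paragraph that promises continued blinding also supplies the figures that make assignment predictable. The study team demonstrably has those figures, since the pharmacy reported the 12:6 split to it and the protocol prints the 22:1 split.

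The two phases also differ sharply in composition. Most TPTD women are assessed when informed staff expect TPTD. Nearly all placebo women come from the earlier phase, randomized before the correction. Any effect of expectation on how symptoms are elicited, or on how a scan or biopsy label is read, would therefore not average out across arms. It would enter the between-group comparisons of Aim 1 and of the Aim 2 biopsy analysis at 3 months. The documents restrict nobody's access to the split, plan no check of blinding, and describe no masked reading of DXA or biopsies.

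**Working it through.** **Inputs (Section 1, randomization error; arm totals also in Section 2).** Intended allocation 28:12, n = 40. First 18 women: 12 placebo, 6 TPTD. Remaining 23: 1 placebo, 22 TPTD.

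**The plan's own totals.** TPTD 6 + 22 = 28; placebo 12 + 1 = 13; total 18 + 23 = 41. These match Section 2.

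**Accuracy of the best guess.** For someone who knows only the split, the best guess is the majority arm, and its accuracy is the majority share:

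- Intended design, always guess TPTD: 28/40 = 70.0%.
- Last 23 women, always guess TPTD: 22/23 = 95.7%.
- First 18 women, always guess placebo: 12/18 = 66.7%.
- Whole trial, placebo for the first 18 and TPTD for the last 23: (12 + 22)/41 = 34/41 = 82.9%. The best constant guess at the final totals is right 28/41 = 68.3% of the time.

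**Share of the trial in the predictable phase.** 23/41 = 56.1% overall; 22/28 = 78.6% of the TPTD arm; 1/13 = 7.7% of the placebo arm.

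**What a comparison by period can show.** For a difference in means with equal variance, information is proportional to n1 × n2/(n1 + n2):

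- First period: 6 × 12/18 = 4.00.
- Second period: 22 × 1/23 = 0.96.
- Pooled, ignoring period: 28 × 13/41 = 8.88.

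On this measure the first period carries 4.00/8.88 = 45% of the pooled information. The second, with one placebo woman, carries almost none. This is only a guide for symptom counts, but it shows that a first-period comparison will be imprecise.

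**Month-12 unblinding.** Once the one late placebo woman is unblinded, the accuracy for women randomized after her rises from about 96% to 100%. This affects Aim 1 only for those still in their own first 6 months at that point. Her position among the 23 is random, so the number may be small or zero.

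**The case against.** The strongest reply is that 95.7% is a base rate and not an unblinding. No individual code is released, the pens cannot be told apart, and nobody but the pharmacist can say which of the 23 women is on placebo. Even the intended design allowed a 70% correct guess. All of this stands. A reader might infer that blinding has ceased to exist for these women; the documents do not support that.

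Three other inferences also go too far.

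- A reader might suppose that the arm can be read from the subject number. The documents mention only a research ID code and a subject identifier, and do not say that these reveal enrolment order.
- A reader might suppose that participants or outside readers know the odds. Nothing available shows this: consent pages are not in the public copy, and biopsies go to other laboratories whose access to the protocol is not described.
- A reader might conclude that the last 23 women should be redrawn at the intended ratio, about 16:7. That would give roughly 22:19 and abandon the stated aim of 28 women starting on active drug. It is a trade-off between designs, and the point does not require it.

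It is also fair that the primary endpoints are relatively robust. Lumbar spine BMD comes from DXA, and hypercalcemia and hypercalciuria rest on laboratory calcium. The symptom checklist is a secondary safety analysis for which Section 2.B already concedes minimal power, and Section 1 calls the study exploratory. This limits the consequences. It does not make the assurance about personnel accurate.

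**Conclusion.** The point holds for study personnel who know the split. For them, assignment under the corrective table is predictable with about 96% accuracy in 23 of 41 women, up from 70% as designed. The protocol therefore claims a protection that its own figures largely remove.

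This rests on two assumptions: that the table was used as described, and that the person concerned knows both the split and that the woman was randomized under it. The first part of that knowledge is documented for the study team. For participants and outside laboratories it is not.

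The figures measure predictability and the imbalance between phases. They do not measure bias in any outcome, and the documents give no basis for estimating it. The direction of exposure is clear: greatest for elicited symptoms and adverse events, less for DXA and laboratory calcium. The month-12 unblinding adds little.

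**What to change.** 1. In Section 1, replace the assurance with a statement that assignment of women randomized under the corrective table is largely predictable to personnel who know the split, while individual codes and pens remain masked. Qualify the double-blind description in Section 2 to match.
2. Have the existing readers analyse DXA, HR-pQCT and biopsy specimens under random codes that hide subject identifier and enrolment date. Read each woman's baseline and 6-month scans together. Each biopsy is a single specimen carrying both label sets, so it needs recoding but no pairing. Arrange this before the readings are made.
3. Do not describe the pooled symptom and adverse event comparison as fully blinded. Show it by randomization period as well, noting that the first-period comparison (6 TPTD against 12 placebo) is imprecise and that the second has one placebo woman.

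The cost is a recoding and batch-reading step that the protocol does not now describe, one extra safety table, and a less favourable account of the blinding. No participant has an additional visit or procedure.
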